### **8.3 Statistical methods**

Part 1: The primary hypothesis is that there is no difference in the results of PFT and rPFT for respiratory assessment of FVC and MIP. We will use a paired sample t-test to determine if the mean test results are comparable between the standard and experimental treatments. We will conduct a qualitative analysis to determine whether the patient, caregiver, and therapist determine the rPFT to be an effective way to conduct tests of breathing function.

Part 2: The primary outcomes will be analyzed to determine if respiratory parameters are closer to the actionable threshold at NIV recommendation and whether QoL is better sustained at this point in individuals in the experimental group. This will be done using a non-parametric two sample test of means, the Wilcoxon-Mann-Whitney rank sum test.

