#### Part 1: Demonstrate the reliability of remote pulmonary function testing, performed via telemedicine, for monitoring respiratory function in patients with amyotrophic lateral sclerosis (ALS)

*Primary Hypothesis:* There is no difference in the results of PFT and rPFT for respiratory assessment of FVC and MIP.

*Secondary Hypothesis:* The respiratory therapist, patient, and caregiver will express confidence in conducting the rPFT, as determined by surveys of procedure acceptance.

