### 1.2 Primary Study Endpoints

Part 1: The primary endpoint is completion of a standard PFT and an experimental rPFT during a single clinic appointment. At the endpoint, study outcomes will include:

- 1) The best FVC and MIP results from that visit's PFT
- 2) The best FVC and MIP results from that visit's rPFT
- 3) Survey responses from study participants.

Part 2: The primary endpoint for each person in the study is the completion of the fifth clinical visit, during which the control arm should have complete data for the following outcomes:

- 1) The results of five PFT administrations at 3 month intervals
- 2) Patient and caregiver monthly surveys

In addition, the experimental group will have engaged in eight additional guided rPFT assessments with the respiratory therapist over the telemedicine interface.

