### **3.2 Exclusion Criteria**

#### Part 1

Patients:

- 1) Cognitive impairment, as judged by the ALS clinic neurologist, that prevents participation in the study.
- 2) ALS Functional Rating Scale (ALSFRS-R) [Cedarbaum1999] score on day of screening of less than or equal to 2 on all of the items for speech, swallowing, and salivation. These items are indicators of bulbar dysfunction, which limits the reliability of PFT administration.

Caregivers: None

Controls: None

Respiratory Therapists: None

Part 2 imposes additional exclusion criteria for patients only.

Patients:

- 3) Use of NIV or diaphragm pacer at time of obtaining informed consent.
- 4) FVC  $\leq$ 50% predicted or MIP  $>$  -60 cm H2O.

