The Air Smart Spirometer works with iPhone and connects via its cable to the headphone input jack. The Air Smart Spirometer has a built-in battery designed to function for at least 2 years or 1 000 single tests. When the battery is drained, dispose of the device as electronic waste. The Air Smart Spirometer is designed to work with disposable and single use FlowMir® turbines. When performing a spirometry test, the user exhales into the turbine. The airflow generated sets a rotor in motion. The Air Smart Spirometer registers the speed of the spinning rotor, converts it and transfers the data to the smartphone with the Air Smart Spirometer app.”

2) GiO 4 Digital Pressure Gauge, Respiralogs

The following information is paraphrased from the user manual, which is included in the “devices” page of the protocol.

“GiO Pressure Gauge is a high accuracy digital gauge that displays pressure measurement in both analog bar and digital reading. The GiO Gauge can be used in various settings and has a wide range of

applications in both medical and non-medical fields. GiO Digital Pressure Gauge is designed to detect and display pressure reading to a high degree of accuracy. This means it may also be sensitive to changes in pressure and is so fast in responding to the changes that you may find it difficult to determine the reading you would like to record. The P&H or Peak and Hold function is a design that captures and holds the display of peak pressure reading. The GiO 4 measures pressures from -60 cm H2O to 0 cm H2O."

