## 7.2 Study Procedures

### 7.2.1 Part 1

On or before the date scheduled for Study 1, a member of the research team who is not part of the ALS clinical team will describe the procedures and receive written informed consent from the patient and caregiver dyad, as well as the respiratory therapist. The participant team undergoes the initial in-person pulmonary function testing, followed 2-3 hours later at the end of the clinical visit by the rPFT. rPFT administration is described in Section 7.4.2. For roughly half of the enrolled participants, the order of assessments is reversed. Following the study procedures, the therapist and patient/caregiver dyad will complete a survey concerning the ease of use and confidence in the rPFT assessment.

Part 1 includes the recruitment of up to 20 practice control participants for validation of the study procedures. They will perform the same procedures as the patient and caregiver, in conjunction with the respiratory therapist.

### 7.2.2 Part 2

On or before the date scheduled for the start of the study, a member of the research team who is not part of the ALS clinical team will describe the procedures and receive written informed consent from the patient and caregiver dyad. The researcher will then collect demographic information for purposes of randomization to an arm of the study: age, gender, and time since symptom onset. The participant team will undergo the initial in-person pulmonary function testing as part of their clinical visit.

Month	0	1	2	3	4	5	6	7	8	9	10	11	12
Exp. Arm (n=20)	C+S PFT	S rPFT	S rPFT	S PFT									
Control Arm (n=20)	C+S PFT	S PFT	S PFT	S PFT									

**Table 1: Part 2 schedule. Participants will be enrolled at month zero, and randomized into a study arm depending on clinical characteristics of age, gender, and time since symptom onset (C). All participants attend clinic (indicated by gray shading) approximately every three months to have PFT administered by a respiratory therapist. Patients in the experimental group will conduct monthly rPFT assessments in the two interim months. Each month, all participants are required to complete the study survey (S).**

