- 3) Short Form 36 (SF-36) [Ware1992]. This is a generic, coherent, and easily administered quality-of-life measures which has been shown to be sensitive for mental and physical health assessment in ALS [Bourke2006, Jackson2001, Bourke2003].
- 4) SAQLI parts E and F (NIV users only). These sections ask about problems that may have arisen due to NIV use and how respiratory symptoms may have been alleviated due to treatment during this period.

Each session concludes with recommendations from the therapist based on the results of respiratory tests. These can include behavioral modifications or recommendation for NIV. Recommendation of NIV is based on a measured FVC  $\leq$ 50% predicted or for dyspnea accompanied by MIP  $>$  -60 cm H2O. This recommendation will be reviewed by the ALS clinic neurologist. If the decision is made to initiate NIV, the ALS clinic physician will provide an order, and the ALS clinic nurse will arrange for initiation of in-home NIV via a third-party vendor according to usual standards of care.

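### Part 1 sets out to show that remote testing is reliable, but its only quantitative analysis is a paired t-test of means with no margin, interval rule or agreement statistic

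*Combined protocol and SAP*

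**What the plan says.** Section 1.1 gives the Part 1 aim as "Demonstrate the reliability of remote pulmonary function testing, performed via telemedicine", and its primary hypothesis as "There is no difference in the results of PFT and rPFT for respiratory assessment of FVC and MIP". Section 8.3 repeats that hypothesis and names the analysis: "We will use a paired sample t-test to determine if the mean test results are comparable between the standard and experimental treatments". The only other Part 1 analysis is a qualitative one of user opinion.

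On the endpoint, section 1.2 says "The primary endpoint is completion of a standard PFT and an experimental rPFT during a single clinic appointment". It then lists the best FVC and MIP from each test among the outcomes, so the paired values will exist.

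Section 7.2.1 provides for both test orders: "For roughly half of the enrolled participants, the order of assessments is reversed". Section 8.1 sets 40 patient/caregiver teams for Part 1 and allows up to 20 practice controls. Section 8.3 does not say whether the controls enter the comparison. The power text in section 8.2 concerns Part 2 outcomes only.

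Two further statements bear on MIP. Section 7.1 says "The GiO 4 measures pressures from -60 cm H 2 O to 0 cm H 2 O". Section 3.2 introduces the FVC and MIP limits with "Part 2 imposes additional exclusion criteria for patients only", so Part 1 has no MIP limit.

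**The concern.** The claim Part 1 hopes to make is the null hypothesis of the test it will use. Failing to reject a null does not establish it, and the plan sets no limit on how large a difference would still be acceptable. A mean comparison also answers a narrower question than reliability, because positive and negative errors in individual patients can cancel. Individual readings matter here: of the Part 2 sessions, section 7.2.2 says "Each session concludes with recommendations from the therapist based on the results of respiratory tests".

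At stake is whether the Part 1 primary conclusion means anything. A biased or widely scattered rPFT could be reported as comparable, and a precise rPFT with a trivial constant offset could be reported as different.

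**Working it through.** **Inputs.** n = 40 pairs (section 8.1, practice controls not counted). Two-sided 5% level (assumed; section 8.3 states none). Normally distributed paired differences (assumed). The documents give no SD for the paired difference, so the main results are in units of that SD. There is no Part 1 power or precision figure to reproduce.

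**1. What non-significance allows.** The statistic is t = d̄ / (s/√40), with 39 degrees of freedom and critical value 2.023. The result is non-significant whenever |d̄| < 2.023 × s/√40 = 0.320 s.

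**2. Chance of missing a real bias.** For a true bias of δ SDs, t is noncentral t with noncentrality δ√40, and P(non-significant) = P(|t| < 2.023).

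| True bias (SDs) | Noncentrality | P(non-significant) |
|---|---|---|
| 0 | 0 | 95% |
| 0.30 | 1.90 | 54% |
| 0.45 | 2.85 | 21% |
| 0.60 | 3.79 | 4% |

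**3. Direction of the effect of scatter.** Take a true bias of 2 units, with illustrative SDs. At SD 5 it is 2/5 = 0.4 SD, non-significant 31% of the time. At SD 20 it is 2/20 = 0.1 SD, non-significant 91% of the time. The noisier device passes more easily.

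**4. Zero bias, any scatter.** P(non-significant) stays at 95% whatever the SD. The 95% limits of agreement are ±1.96 SD: ±9.8 units at SD 5 and ±39.2 at SD 20. The t-test result does not separate the two cases.

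**5. The reverse failure.** A bias of one third of an SD is significant 1 − 0.46 = 54% of the time, however small it is in measurement units (for example, 1 point at an assumed SD of 3).

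**6. Sensitivity to the analysis set.** If all 20 practice controls were pooled in, giving 60 pairs, the 0.3-SD bias would be non-significant 37% of the time instead of 54%. The size changes; the conclusion does not.

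**7. What an equivalence rule on the mean would cost.** The rule is met if d̄ ± 1.685 × s/√40 (the 90% interval) lies wholly within ±M. For illustration only, M = 5 points of FVC % predicted with zero true bias. By simulation the rule is met about 97%, 86% and 66% of the time at assumed SDs of 8, 10 and 12. In general, 80% power at zero bias needs a margin of at least about 0.47 SD.

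**The case against.** The case on the other side limits how far the point can be taken.

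- A reader might infer that the plan treats p > 0.05 as proof of agreement. It does not say so. What the documents establish is that no criterion is stated, and the probabilities above apply if non-significance is used.
- It is tempting to say that the t-test ignores scatter. It does not: the SD of the differences is in its denominator. The test does not assess scatter as an outcome, and scatter pushes the result in the wrong direction.
- Section 1.2 words the endpoint as completion of both tests, which might suggest that agreement data are not captured. They are, in the outcomes listed beneath it.
- A reader might conclude that Part 2, or patient care in it, depends on a faulty Part 1 result. The documents do not make Part 2 conditional on Part 1, and section 7.2.2 has the clinic neurologist review each recommendation for ventilation.
- The pressure gauge's range might suggest that the MIP comparison is bound to fail. Off-scale readings are possible, but their frequency cannot be derived. Sections 8.1 and 3.2 allow a patient to be in both parts and require MIP at -60 or stronger for Part 2. That does not fix the patient's MIP on the Part 1 day, since the order and gap between parts are not given.

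All five limits stand. None supplies a margin, an interval rule or an agreement measure, so the gap between aim and analysis remains.

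**Conclusion.** The concern holds. The stated test cannot, by a non-significant result, establish the stated conclusion, and the plan offers no other quantitative basis for it. The probabilities rest on 40 patient pairs, a two-sided 5% level and normal differences; none in the table needs an assumed SD. Results in measurement units are illustrations.

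The damage is confined to the validity of the Part 1 primary conclusion. No data are lost, but a margin chosen after the results are seen would carry little weight, so the change should be made before Part 1 is analysed.

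**What to change.** In section 8.3, replace the t-test as the basis for the Part 1 conclusion. Suggested text:

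> For the patient pairs, the primary Part 1 analysis is the mean paired difference (rPFT minus PFT) with its confidence interval, and the Bland-Altman 95% limits of agreement with confidence intervals, with test order as a factor. Agreement in means will be claimed only if the 90% confidence interval of the mean difference lies within a margin justified and fixed before analysis; otherwise only estimates are reported. The limits of agreement are descriptive, and no claim about individual readings will be made from the mean comparison, unless a bound on the limits was fixed before analysis. Conclusions for FVC and MIP are drawn separately. The number of off-scale rPFT readings for MIP will be reported, and their handling specified before analysis.

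The investigators must choose the margin and any bound; the documents give no basis for either. Off-scale MIP readings should not be entered as -60, or dropped, and the result then presented as agreement: the first substitutes the gauge's limit for the reading, and the second selects pairs on the outcome. The plan should also say that practice controls are outside this analysis.

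**Cost.** Same participants, same procedures and a little more analysis; adjusting for order uses one degree of freedom. The real downside is that agreement is harder to claim, as step 7 of the working shows. If no margin can be justified, Part 1 reports estimates and limits without a claim of agreement.

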#### Part 2: Monitor more closely the course of respiratory function over time in patients with ALS by using remote pulmonary function testing, performed via telemedicine.

*Primary Hypothesis:* Home respiratory assessment enables thresholds for Non-invasive ventilation (NIV) recommendation to be met in the experimental group significantly closer to the initiation criteria, at a time when quality of life is higher, compared to the control group.

*Secondary Hypothesis:* Telemonitoring of respiratory health in the experimental group will maintain higher quality of life, and lengthen survival.

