## 2.0 Background

### 2.1 Scientific Background and Gaps

#### Non-invasive ventilation (NIV) lengthens survival and improves QoL for patients with ALS.

According to the Quality Measurement Set put forth by the American Academy of Neurology (AAN), two parameters of high importance in ALS care are monitoring of respiratory function and management with NIV [Miller2013]. The practice parameter of the AAN regarding ALS care states that NIV is effective in prolonging survival and slowing the rate of respiratory decline [Miller2009]. NIV has been documented to have a positive effect on QoL in the areas of sleep quality, daytime sleepiness, physical fatigue, and

depression [Butz2003]. NIV is recommended when a patient presents with either an FVC≤50% predicted or a MIP > -60 cm H2O [Miller2009]. It is recommended that PFTs be done at least once every three months, and that doctors discuss options for NIV support regularly.

The multidisciplinary clinical model may not provide optimal management for patients with rapidly progressing respiratory symptoms.

Although disease course varies substantially, some patients experience rapid respiratory decline. In prospective study of 38 newly diagnosed patients, half presented with chronic hypoventilation after one year, necessitating the introduction of NIV [LoCoco2006]. The authors suggest that efforts should be made to evaluate pulmonary function in these patients at least once every month. Furthermore, it has been shown that early initiation of NIV at an FVC threshold of 65% predicted was associated with a significant increase in the median time from ALS diagnosis to death [Lechtzin2007]. The current practice of quarterly respiratory assessment may leave some individuals in danger of developing to untreated respiratory insufficiency or beginning treatment later than would be optimal or other more scientific wording.

Telemedicine has impacted other areas of neurology, but is understudied for efficacy in ALS.

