### **8.2 Sample size determination**

Our sample size is predetermined based on our subjective ability to recruit patients within the time frame of the study. Power analysis was based on studies of FVC decline. Lo Coco et al., [LoCoco2006], showed that 50% of study participants dropped below 50% predicted FVC in one year. Given that our exclusion criteria for Part 2 will reject many of the 37% of individuals in their study who were "slow progressors," we estimate that 75% of patients enrolled in our study will meet the respiratory criteria to recommend NIV. This results in a sample size per arm of n=15, which provides 80% power to detect a difference in mean outcome between the two groups if the effect size is found to be 0.95.

Assuming a monthly change in FVC of  $3.5 \pm 3.4\%$  found by Schiffman et al. [Schiffman1993], we conducted 10,000 Monte-Carlo simulations of 40 participants declining at this rate for 12 months. Half were sampled once every three months, and half were sampled every month.  $80.6 \pm 6.3\%$  of simulated participants met the requirements for NIV recommendation, in roughly equal proportions across groups. The average FVC at recommendation was 47.0% predicted in the experimental group, and 43.4% predicted in the control group. The effect size of the difference in FVC between groups was  $.964 \pm .343$ . Similarly, the two measures of QoL obtained at NIV recommendation are powered with an 80% chance to detect improvement of quality of life in the experimental group if the effect size is also found to be 0.95. This corresponds to a mean score difference of 1.52 on the SAQLI, assuming a standard deviation of 1.6 [Flemons1998]. Although there is no published data on the standard deviation of MDRS-D scores, the range and format of questions is similar enough to estimate a comparable difference between groups is needed.

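### Part 2 tests several primary outcomes at NIV recommendation with no alpha, sidedness, order or success rule, so the plan does not say what result counts as success

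*Combined protocol and SAP*

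**What the plan says.** All references are to the combined protocol and SAP.

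- **Section 8.3** speaks of Part 2 primary outcomes in the plural: "The primary outcomes will be analyzed to determine if respiratory parameters are closer to the actionable threshold at NIV recommendation and whether QoL" holds up better. The test is the Wilcoxon-Mann-Whitney rank sum test. The individual variables are not listed.
- **Section 1.1** gives the Part 2 primary hypothesis as recommendation "significantly closer to the initiation criteria, at a time when quality of life is higher, compared to the control group". Quality of life returns in the secondary hypothesis: "Telemonitoring of respiratory health in the experimental group will maintain higher quality of life, and lengthen survival".
- **Section 1.2** states that "The primary endpoint for each person in the study is the completion of the fifth clinical visit". It then lists data to be complete by that visit and names no variable on which the arms are compared.
- **Section 2.1** supplies the two respiratory parameters that have a threshold: "NIV is recommended when a patient presents with either an FVC≤50% predicted or a MIP" criterion is met.
- **Section 8.2** says 15 per arm "provides 80% power to detect a difference in mean outcome between the two groups if the effect size is found to be 0.95". It simulates FVC only, then adds that "the two measures of QoL obtained at NIV recommendation are powered with an 80% chance to detect improvement of quality of life", and discusses SAQLI and MDRS-D. It gives no power for MIP.
- **Section 7.2.2** adds SF-36 to the monthly survey, described as among the "generic, coherent, and easily administered quality-of-life measures".

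No section gives an alpha, a sidedness, an order of testing, an adjustment, or a rule on whether one or all outcomes must succeed.

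**The concern.** Once there is more than one primary outcome, the success rule fixes the trial's operating characteristics. If any one favourable test counts, the chance of at least one false positive exceeds the level of each test. If all must be favourable, error is controlled, but the chance of success is below the power of each test. The plan leaves the choice open. Following it as written, one favourable p-value among several could be reported as a positive trial. Equally, a reader who takes the hypothesis as a joint claim has no power figure for it. With about 15 evaluable patients per arm, either outcome is a practical possibility.

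**Working it through.** **Inputs.** From Section 8.2: 75% expected to reach the NIV criteria, 15 evaluable per arm, effect size d = 0.95, 80% power. From Table 1: 20 per arm. Assumed, because the documents are silent: 5% per test (one- and two-sided) and a common correlation ρ between outcomes of 0 to 0.9. The count of four (FVC, MIP, SAQLI-D, MDRS-D) is inferred; two (one respiratory, one QoL) is the narrowest plural reading.

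**Step 1: the plan's own figure.** Evaluable patients: 20 × 0.75 = 15 per arm. SAQLI difference: 0.95 × 1.6 = 1.52, as stated. For the t-test, the noncentrality is d√(n/2) = 0.95 × √7.5 = 2.60 on 28 degrees of freedom. For the Wilcoxon test, n is multiplied by 3/π (15 × 0.955 = 14.3).

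| Power, n = 15 per arm, d = 0.95 | one-sided 5% | two-sided 5% |
|---|---|---|
| t-test | 81.4% | 70.9% |
| Wilcoxon | 79.7% | 68.8% |

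The stated 80% is reproduced per outcome at one-sided 5%, and not at two-sided 5%.

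**Step 2: any one success suffices.** Under independence the family-wise error is 1 − 0.95^k: for k = 4, 1 − 0.8145 = 18.5%; for k = 2, 1 − 0.9025 = 9.8%. For correlated outcomes (one-sided form) it is 1 − ∫φ(u)·Φ((1.645 + √ρ·u)/√(1−ρ))^k du. Ranges below run from one-sided to two-sided.

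| ρ | four tests | two tests |
|---|---|---|
| 0 | 18.5% | 9.8% |
| 0.3 | 16.4-17.4% | 9.3-9.5% |
| 0.5 | 14.4-15.6% | 8.8-9.1% |
| 0.7 | 12.0-13.0% | 8.0-8.3% |
| 0.9 | 8.8-9.4% | 6.8-7.0% |

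Simulating four exact Wilcoxon tests with 15 per arm gives 8.6% (ρ = 0.9) to 17.8% (ρ = 0, one-sided); the exact test is slightly conservative.

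Two-sided error counts false findings in either direction. A false claim of benefit among four independent two-sided tests has probability 1 − 0.975^4 = 9.6%, or 7.7% at ρ = 0.5. For two independent tests it is 1 − 0.975² = 4.9%. The single-test comparator is 2.5%.

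**Step 3: all must succeed, 80% power each.** Under independence joint power is 0.8^k: 0.8^4 = 41%; 0.8² = 64%. With correlation it is ∫φ(u)·Φ((0.842 + √ρ·u)/√(1−ρ))^k du.

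| ρ | four outcomes | two outcomes |
|---|---|---|
| 0 | 41% | 64% |
| 0.3 | 50% | 67% |
| 0.5 | 56% | 69% |
| 0.7 | 62% | 71% |
| 0.9 | 70% | 75% |

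This gives MIP the same 80%, which the plan does not claim. Simulated directly with the Wilcoxon test at 15 per arm and d = 0.95 on all four, joint power is 39-68% one-sided and 20-53% two-sided.

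**Step 4: what other remedies would cost.** Bonferroni over four (0.05/4 = 0.0125) leaves Wilcoxon power per outcome at about 57% one-sided or 46% two-sided. Restoring 80% needs about 24 or 28 evaluable per arm, which is 24/0.75 = 32 or 28/0.75 ≈ 38 enrolled. Four co-primaries with 80% joint power under independence need about 26 or 31 evaluable, or 35 or 42 enrolled per arm.

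**The case against.** The best defence is that the hypothesis in Section 1.1 couples closeness to the criteria with higher quality of life, so it can be read as requiring both. Under that reading error is not inflated, and Section 8.2 never promised a joint power. This stands as far as it goes: no stated figure is contradicted. It does not settle the matter, because Section 8.3 does not adopt the joint rule and the power for that rule is absent.

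The count of four is also inferred, since Section 8.3 speaks only of respiratory parameters and QoL. That is fair, and it is why the two-outcome figures are shown; the gap narrows but remains.

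This is also a small single-clinic study whose sample size Section 8.2 says was set by recruitment. That argues against remedies that need more patients, but naming a primary outcome needs none.

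Finally, putting FVC first is a judgement. It separates a coupled hypothesis and makes QoL conditional on FVC. Section 7.2.2 also allows recommendation for dyspnea with a MIP criterion, so FVC at recommendation need not lie near 50%, and the Section 8.2 simulation reports FVC only. This stands as a caution. Co-primaries or a split alpha would also close the gap, at the cost in Step 4.

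**Conclusion.** The concern holds as an unspecified success rule. At an assumed 5% per test, four outcomes give a family-wise error of about 9% to 18.5% if any success suffices, or joint power of about 41% to 70% if all must succeed. Two outcomes give about 7-10% or 64-75%. The ranges reflect correlations from 0.9 to 0, which the documents do not give; the power figures assume 80% for every outcome.

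Three stronger readings are tempting but unsupported:

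- A reader might infer that the plan sets a 5% error rate and breaches it. No alpha is stated; 5% is this review's assumption.
- A reader might infer that the stated 80% is false. It is given for individual outcomes (FVC and the two QoL measures) and is reproduced at one-sided 5%. No joint power is claimed, so none is contradicted.
- A reader might count SF-36 as a fifth primary outcome. Section 8.2 speaks of two QoL measures at NIV recommendation and discusses SAQLI and MDRS-D; SF-36 fits the secondary QoL hypothesis at least as well.

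The point should be corrected before analysis, since it governs what the trial may claim.

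**What to change.** In Sections 1.2 and 8.3:

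1. Name FVC % predicted at NIV recommendation as the single Part 2 primary outcome. It is the only outcome simulated in Section 8.2.
2. Test SAQLI-D and then MDRS-D at NIV recommendation in fixed sequence, each at the full alpha and only if the preceding test succeeds. Label MIP and SF-36 supportive.
3. State alpha and sidedness, and restate the power in Section 8.2 to match: for the planned Wilcoxon test with 15 per arm and d = 0.95, about 80% at one-sided 5% or about 69% at two-sided 5% (t-test 81% and 71%).

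The cost is wording; no patients are added and the first test gives up no alpha. There are three downsides. QoL claims depend on FVC succeeding first: at 80% power each, the chance of reaching and winning SAQLI-D is 64-75%, and of MDRS-D as well 51% (0.8³, independent) to 72% (correlation 0.9). MIP and SF-36 carry no confirmatory claim. If two-sided 5% is chosen, the power for FVC falls about 11 points below the stated 80% at the current sample size, and the plan should say so.
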